Title: Effect of health education on promoting influenza vaccination health literacy among primary school students: a cluster randomized controlled trial protocol

NCT number: NCT06048406

Document date: 01 September 2023

INTRODUCTION

The Influenza virus, known for its mutability and potent infectivity, poses a significant health risk. Recent trends indicate an escalating incidence of influenza in China, thereby posing a substantial threat to public health.^{1,2} According to national influenza surveillance data, each October marks the onset of the winter and spring influenza epidemic seasons across various regions in China.^{3,4} Currently, the most effective preventative measure against influenza is vaccination.⁵ Seasonal influenza vaccinations have demonstrated efficacy in reducing the risk of influenza infection and severe complications across all age groups.⁶ Seasonal influenza epidemics often precipitate outbreaks in densely populated areas such as schools, childcare institutions, and nursing homes.⁶

Health literacy, defined as an individual's capacity to acquire, comprehend, and utilize basic health information and services for informed health decisions, plays a pivotal role in vaccination uptake.^{7,8} Enhancing vaccine health literacy can potentially augment vaccination willingness and mitigate vaccination hesitancy.⁹ Therefore, improving the population's awareness, attitudes, and behaviors towards influenza vaccination health literacy is integral to the successful implementation of influenza

prevention and control measures and strategy development.

While numerous studies have investigated the broader implications of health education interventions on vaccination awareness and rates, there remains a distinct lack of focused research specifically targeting primary school students, especially within the context of China.¹⁰⁻¹² The unique age group, characterized by their transitional cognitive abilities and susceptibility to influence, may respond differently to health literacy interventions than other age cohorts. Moreover, regional differences, cultural practices, and local health infrastructure in China might further impact the effectiveness of such interventions. Thus, this study aims to investigate the influence of health education on influenza vaccination rates and the level of influenza vaccination health literacy among fourth and fifth-grade primary school students. The methodological approach will involve a cluster randomized trial with schools serving as the unit of analysis. The findings will provide a scientific basis for future interventions.

METHODS AND ANALYSIS

Study objectives

This study seeks to explore the impact of health education interventions on vaccination and influenza vaccination awareness among senior primary school students. By evaluating the impact of health education on the seasonal influenza vaccination rate and the level of influenza vaccination health literacy, we aim to provide a scientific foundation for regional influenza prevention and control

strategies. The specific objectives of this research are: 1) To ascertain the rate of influenza infection, the status of influenza vaccination, and the level of health literacy related to influenza vaccination among primary school students in Dongguan City. 2) To compare and contrast the influenza vaccination rate and the level of influenza vaccination health literacy between the experimental and control groups, thereby evaluating the impact of health education intervention on these parameters. 3) To assess the efficacy of influenza vaccine immunization among primary school students in Dongguan City.

Study design

The proposed study is a cluster randomized controlled trial. Two administrative districts, one in the central urban area and the other in the non-central urban area of Dongguan, will be selected for this study. Within each district, ten primary schools will be randomly selected, with half designated as intervention group schools and the remaining half as control group schools. This results in a total of twenty primary schools, evenly split between the intervention and control groups.

The intervention group will receive a health education intervention focused on influenza vaccination, while the control group will continue with their routine school health education. The intervention period for this study is projected to last approximately three to four months. Data collection will conduct at the onset and conclusion of the intervention period. The primary outcomes of interest are the differences in influenza vaccination rates and influenza vaccination health literacy levels between the experimental and control groups, which will be used to evaluate

the effectiveness of the intervention. The overview of the study procedure is shown in the Figure 1.

Study sample

Study participants are primary school students in grades 4 to 5 in Dongguan City.

Inclusion criteria include: 1) Primary school students within the age range of 7-12 years. 2) Students and their parents who voluntarily agree to participate in the study and provide signed informed consent. 3) Permanent residents of Dongguan City who are expected to complete the project without transferring schools during the study period.

In addition, individuals with contraindications to influenza vaccination, who have recently received an influenza vaccination, diagnosed with influenza or confirmed as influenza-like cases at the commencement of the study, or unwilling to participate in the project, will be excluded.

Sampling method

The study employs a multi-stage cluster sampling method. In the first stage, one central urban area (tentatively identified as Dongcheng Street, which oversees 31 primary schools) and one non-central urban area (tentatively identified as Gaobu Town, which oversees 13 primary schools) will be randomly selected, reflecting the urban-rural structure of Dongguan City. In the second stage, ten primary schools will be randomly selected from each administrative district, with five designated as intervention group schools and the remaining five as control group schools. This results in a total of twenty primary schools, evenly split between the intervention and

control groups. In the third stage, two classes from each of the two grades (fourth and fifth grades) are randomly selected from each of the twenty selected schools using a cluster sampling method, with surveys conducted at the class level. Each school comprises a minimum of 152 students. Schools with 152 students will have one additional class randomly selected. The final estimated total sample size is projected to be 3036. Random sampling and randomized grouping are achieved using computer software to generate random numbers. The sample size is determined using the following formula:

$$n = \frac{\left\{ z_{1-\alpha/2} \sqrt{2(m-1)\rho + 2} + z_{\beta} \sqrt{m\rho + 1} \right\}^2 * \{p_1(1-p_1) + p_2(1-p_2)\}}{(p_1 - p_2)^2}$$

where: n is the desired sample size for each cohort, $z_{1-\alpha/2}$ is the value corresponding to the accepted Type I error rate (eg $z_{1-\alpha/2}$ about 1.96 for an error rate of 0.05), z_{β} is the value corresponding to the desired statistical power, e.g., for a power of 0.8, z_{β} is approximately 0.84. m is the size of each cohort, ρ is the intra-group correlation coefficient, p_1 is the expected outcome rate in the test group (ie, influenza vaccination rate), and p_2 is the expected outcome rate in the control group. Based on the assumption that the anticipated influenza vaccination rate is 80% in the intervention group and 50% in the control group, the estimated sample size, denoted as 'n', is 138 students per school.^{13, 14} This implies that approximately 138 primary school students are required for each group, yielding a total sample size of 2760 individuals. To account for potential sample attrition, the sample size is expanded by 10%, resulting in a final estimated total sample size of 3036 for statistical analysis.

Intervention methods

The intervention group will receive a health education intervention focused on

influenza vaccination literacy, while the control group will continue with their standard school health education without any additional intervention. An influenza vaccination health education including topics such as the importance of influenza vaccination, benefits of vaccination, and vaccination methods, will be developed and reviewed by an expert group. The package for the intervention group will include educational activities, distribution of promotional materials, vaccination services, and distribution of vaccination souvenirs. The details are as follows:

1) Educational activities include classroom lectures and parent meetings. Medical professionals or public health experts will be invited to deliver lectures at the school, providing detailed information on the role and benefits of influenza vaccination and the risks of influenza. Teachers and relevant school staff will be trained to understand the importance of influenza vaccination, reinforcing these messages in everyday teaching. Content about influenza vaccines will be incorporated into school health education courses, facilitating student learning about influenza vaccines. In addition, Teachers will discuss the importance of the flu vaccine at parent meetings, encouraging parents to facilitate their children's vaccination.

2) Promotional materials include educational booklet, animated videos, vaccination service and vaccination souvenirs. Educational booklet will be designed and distribute to students to raise their awareness of flu vaccines. Animated videos will be created to explain the effects of flu vaccines and the benefits of vaccination in an easy-to-understand manner. These videos will be played on school TVs or computers, and students will be organized to watch them. Influenza vaccination services will be provided to students who have no contraindications to influenza vaccination, are in

good health, and are 4-6 months post their last influenza vaccination, based on the principle of informed consent, voluntariness, and self-payment. 'Epidemic Prevention Little Guards' medals will be created and distributed to vaccinated students as a commemorative incentive to encourage vaccination.

Intervention time

Staff of the affiliated street Center for Disease Prevention and Control (CDC) will visit the school in the first month to implement intervention activities using the health education intervention package. The intervention period will commence in September 2023 and conclude in February 2024, resulting in a total intervention duration of approximately three to four months. The specific intervention process is as follows: 1) At the start of the semester (early intervention stage in September 2023), initiation activities will be conducted. The investigators will introduce the study to teachers and students, and medical professionals or public health experts will be invited to deliver classroom lectures at the intervention group schools. Baseline data will be collected at this stage. 2) During the intervention period (September 2023 – January 2024), the intervention group will follow the health education intervention toolkit to conduct intervention activities. 3) At the conclusion of the semester (February 2024), follow-up data will be collected. The intervention timeline is shown in the Figure 2.

Data collection and analysis

Questionnaire surveys will be administered to students and parents before and after

the intervention, using self-completion. The questionnaire design, which is informed by similar research literature (Appendix 1 & 2), will undergo evaluations for reliability and validity. The questionnaire will include the following content: 1) Socio-demographic characteristics (name, age, sex, class, residential address, parents' educational level, occupation, family income); 2) Personal history (basic disease history, allergy history, and personal history); 3) Influenza vaccination health literacy level. The health literacy level concerning influenza vaccination will be assessed across four dimensions: knowledge, attitude, behavior, and skills related to influenza vaccination. Details of these four dimensions include knowledge of basic facts about the influenza vaccine (such as its efficacy, vaccination frequency, and side effects), attitudes towards the influenza vaccine (including perceptions of its efficacy and safety), behavioral characteristics related to influenza vaccination (such as willingness to be vaccinated, vaccination status, and timing of vaccination), and sources of information about the influenza vaccine.

Confirmation of influenza and surveillance of influenza-like cases

Influenza cases are characterized by initial symptoms such as fever, headache, myalgia, and general malaise, with body temperatures potentially reaching 39-40°C. Patients may experience chills, muscle and joint pain, fatigue, loss of appetite, nasal congestion, runny nose, substernal discomfort, facial flushing, and conjunctival hyperemia. Confirmed cases must have one or more of the following positive pathogenic test results: influenza virus nucleic acid test, influenza antigen test, influenza virus culture isolation, and a four-fold or greater increase in the level of influenza virus-specific IgG antibody in the convalescent and recovery period double sera compared to the acute stage.

Confirmed cases of influenza will primarily be identified through the municipal CDC influenza surveillance network. Furthermore, influenza-like illness (ILI) is defined as instances of fever (body temperature $\geq 38^{\circ}\text{C}$) accompanied by either a cough or sore throat, with epidemiological evidence or a positive influenza rapid antigen test, and excluding other diseases that cause influenza-like symptoms. The fever should occur within the current acute febrile illness period. Body temperature identification includes self-measurement by patients and temperature detection by medical institutions. Identification of ILI cases can be achieved through establishment of a case reporting system in schools or student or parent self-report. The case reporting system in schools involves training school medical staff and teachers to understand the definition and reporting methods for ILI cases. When students exhibit influenza-like symptoms (such as fever, cough, sore throat, or other symptoms), the school's medical staff or teachers will report these cases. Concurrently, a morning inspection and registration system for illness-related absenteeism will be implemented. Cases identified through the student or parent self-report will be obtained by questionnaires, telephone calls, emails, or online platform reports.

Study outcomes

Primary outcomes include the influenza vaccination rate and the influenza vaccination health literacy level. The influenza vaccination rate will be calculated as the number of vaccinated individuals divided by the total number of individuals, multiplied by 100%. Regarding the influenza vaccination health literacy level, each correct answer for the scale will be scored as one point, with incorrect answers receiving no points. Based on the scores, health literacy levels will be categorized as low, medium, or

high.

Secondary outcomes include influenza incidence, the ILI incidence and the influenza vaccine protection rate. The influenza incidence will be calculated as the number of individuals diagnosed with influenza divided by the total number of individuals, multiplied by 100%, The ILI incidence will be calculated as the number of ILI cases divided by the total number of participants, multiplied by 100%. The influenza vaccine protection rate will be calculated as the difference between the incidence rate in unvaccinated individuals and the incidence rate in vaccinated individuals, divided by the incidence rate in unvaccinated individuals, multiplied by 100%.

Statistical analysis plan

Continuous variables will be described using means \pm standard deviation or median (interquartile range), and comparisons will be made using two independent samples t-tests or Wilcoxon rank-sum tests. Categorical variables will be described using frequency and composition ratios, and rate comparisons will be conducted using Chi-square tests or Fisher's exact probability method. The association between the level of influenza vaccination health literacy and vaccination willingness will be analyzed using multivariate logistic regression.

Quality control

Quality Control will be conducted in accordance with the requisite quality control standards, with dedicated on-site quality control personnel assigned to oversee investigation and evaluation. These personnel should be proficient in various testing technical requirements and quality control points, and familiar with the on-site

organizational process and division of responsibilities. Their primary responsibilities include: on-site inspection of various investigation and evaluation operational processes, immediate correction of identified issues; on-site review and re-testing of collected information, with rectification based on re-test results; collection, summarization, and analysis of investigation and evaluation quality control issues, with timely reporting and sharing of these issues.

Patient and public involvement

Students and their parents, teachers, and/or the public were not involved in the design, or conduct, or reporting, or dissemination plans of this study.

ETHICS AND DISSEMINATION

This study follows the Declaration of Helsinki and the Chinese clinical trial research ethics and regulations. Before the commencement of the project, ethical approval has been sought from the Ethics Committee of the School of Public Health, Sun Yat-sen University. The research process respects the autonomy of students and schools. The primary schools selected for this study have an equal probability of being assigned to either the intervention or control group, ensuring the impartiality and fairness of the research. Prior to the initiation of the study, the lead researcher provided an overview of the study's purpose, procedures, and potential risks. Comprehensive informed consent forms, detailing the study's intent, processes, and potential risks, will be handed to both students and their guardians, and participation is strictly voluntary. Data confidentiality is ensured through anonymization and restricted access, with only the core study team able to view raw data. Provisions are also in place to address any adverse reactions or events related to the study or vaccination.

Findings from the study will be made accessible to both the scientific community and the public. Results are slated for submission to peer-reviewed journals, ensuring validation and broader reach within the research community. Beyond academic circles, outcomes will be relayed to key stakeholders, including school officials, health departments, and community leaders, fostering informed decisions at the grassroots level. Additionally, feedback sessions, online postings, and conference presentations are avenues being considered to ensure widespread dissemination and awareness.

Funding: This work was supported by the Department of Education of Guangdong Province (grant number: 51000-42240006).

REFERENCES

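### Schools get their arm before classes are drawn, and nothing places family consent and exclusions before arms are known, so entry to each arm can depend on allocation

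*Combined protocol and SAP*

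**What the plan says.** **Order of the stages (Sampling method).** In the second stage ten schools are drawn per district, "with five designated as intervention group schools and the remaining five as control group schools". Classes come next: "In the third stage, two classes from each of the two grades" (grades four and five) "are randomly selected from each of the twenty selected schools using a cluster sampling method". On mechanism, the section says: "Random sampling and randomized grouping are achieved using computer software to generate random numbers".

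**Who may enter (Study sample).** One inclusion criterion is "Students and their parents who voluntarily agree to participate in the study and provide signed informed consent". Among those excluded are children with a contraindication and those "who have recently received an influenza vaccination, diagnosed with influenza or confirmed as influenza-like cases at the commencement of the study, or unwilling to participate". No time window is attached to the word recently.

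**Consent (Ethics and Dissemination).** "Comprehensive informed consent forms, detailing the study's intent, processes, and potential risks, will be handed to both students and their guardians". When this happens relative to allocation, or to its disclosure, is not said.

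**Start of the study (Intervention time).** The early stage in September 2023 contains the introduction of the study to teachers and students, the expert lectures at intervention schools, and baseline collection.

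**Concealment and blinding (Appendix IV, SPIRIT checklist).** Item 16b on allocation concealment refers to pages 7-8. The sampling text describes random number generation but no concealment step. Items 17a and 17b on blinding are marked N/A.

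**Analysis (Statistical analysis plan).** Comparisons use t-tests or Wilcoxon tests and chi-square or Fisher tests. The only regression relates health literacy to vaccination willingness. Checklist item 20b, which covers adjusted analyses, is N/A.

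**The concern.** Randomising schools balances the schools. It does not balance the families who enrol afterwards if those families, or the staff who approach and screen them, already know the school's arm.

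This trial is exposed because two of the entry filters lie very close to the first primary outcome. A family unwilling to join a vaccination-promotion study may well be one that would not vaccinate, and exclusion for recent vaccination removes children according to vaccination behaviour. The intervention is also conspicuous: lectures, parent meetings, a vaccination service and medals for vaccinated students. If hesitant families decline more often where they know vaccination is being promoted, the enrolled intervention group will have a higher vaccination rate even if the programme does nothing.

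The planned analysis offers no protection, because the between-arm tests make no baseline adjustment. A larger sample would not help either, since this is bias and not sampling error.

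**Working it through.** **1. The sequence, step by step**

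| Step | Where the plan puts it | Before arms are known? |
|---|---|---|
| Schools drawn and designated to arms | Sampling method, stage two | This is the allocation |
| Classes drawn by computer | Sampling method, stage three | After designation |
| Study introduced, baseline taken | Intervention time, September stage, with the lectures | Not stated |
| Exclusions applied | Study sample, at commencement for influenza and ILI | Not stated |
| Consent obtained | Ethics and Dissemination, undated | Not stated |

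Consent and screening concern students in sampled classes, and classes are sampled after arms are designated. The natural reading is that both follow allocation. That is an inference from the order; no sentence says it. Nor does any sentence say that arms are withheld from families, schools or recruiters until consent and screening are complete.

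The class draw can be set aside. If the computer draw is followed, knowing the arm cannot change which classes come up. The exposed steps are consent and the individual exclusions.

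**2. How large the effect could be**

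The plan gives no consent rate, so no figure of its own can be reproduced on this point. Inputs:

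- From the Sampling method section: expected vaccination rates of 80% and 50%, a planned difference of 80 − 50 = 30 points.
- Assumed: no true effect. A share w = 0.50 of families would vaccinate (the plan's control rate) and do so; the others do not.
- Assumed: consent in control schools is unrelated to willingness, so the control rate stays at 50%.
- Assumed: in intervention schools, willing families consent at a = 0.90 and unwilling families at b, varied from 0.90 down to 0.60.
- Assumed: the denominator of the vaccination rate is the enrolled students.

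Enrolled vaccination rate in intervention schools = w·a / (w·a + (1 − w)·b). Overall consent there = w·a + (1 − w)·b.

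| b | Calculation | Intervention rate | Spurious difference | Share of planned 30 | Overall consent |
|---|---|---|---|---|---|
| 0.90 | 0.45/(0.45+0.45) | 50.0% | 0 points | 0% | 90% |
| 0.80 | 0.45/(0.45+0.40) | 52.9% | 2.9 points | 10% | 85% |
| 0.70 | 0.45/(0.45+0.35) | 56.3% | 6.3 points | 21% | 80% |
| 0.60 | 0.45/(0.45+0.30) | 60.0% | 10.0 points | 33% | 75% |

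The number of students appears nowhere in the formula, so the spurious difference does not shrink as the sample grows.

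**3. Does the remedy affect the sample size?** The plan's totals are 138 × 20 = 2760 and 2760 × 1.10 = 3036. Neither depends on when consent is taken, so resequencing leaves both unchanged.

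Differential use of the recent-vaccination exclusion is not quantified, because the documents give nothing on which to base a rate.

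**The case against.** The strongest reply is that the stages describe a sampling scheme and not a calendar. Listing designation before the class draw does not show when anyone learns the arm, and recruitment bias needs disclosure. The plan would be sound if allocation were generated in stage two and withheld until consent was complete. Surveys are said to be administered before and after the intervention, and the ethics section says an overview of the study was given beforehand. Figures 1 and 2 and the consent materials could not be read here and might settle the order.

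Much of this stands. It limits the point to an open risk and rules out several stronger readings that a reader might infer:

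- *That the plan states consent follows allocation.* It does not; consent is never dated against allocation or its disclosure.
- *That drawing classes after allocation itself causes selection.* The draw is random by computer, so it does not.
- *That nobody is blinded.* The checklist column records the page where an item is addressed. N/A shows that blinding is not addressed, not that recruiters know the arm.
- *That the exclusions will be applied differently by arm.* The criteria are the same for both arms. The undefined word recently leaves room for judgement, but nothing shows it would be used unevenly.
- *That a bias of 6 to 10 points is to be expected.* Those values need assumed consent rates; equal consent gives zero.

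The reply does not close the gap. A survey before the intervention is not the same as consent before disclosure, and equal assignment probability for schools says nothing about which families enrol later. A team following the written plan could recruit with arms known and breach none of it.

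**Conclusion.** The concern holds as a risk that the design leaves open. Schools are designated to arms before classes are drawn, the study introduction and baseline share a stage with the intervention lectures, and no text places consent and exclusions before arms are known or describes concealment. Entry can therefore depend on allocation, through filters tied directly to the vaccination-rate outcome and with no planned adjustment.

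The size is unknown. Under the stated assumptions it runs from 0 to 10 points, or up to one third of the planned 30. It could be larger if unwilling families consented at less than 60%, and it vanishes if consent is unrelated to willingness in both arms. The conclusion rests on inferred consent timing; a clear statement that arms are withheld until enrolment is complete would answer it. The change should be made, because later analysis cannot reliably repair this bias and resequencing prevents it cheaply.

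**What to change.** State the order explicitly in the Sampling method and Intervention time sections:

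1. Select the 20 schools and draw the classes.
2. Apply the exclusions by one written rule, identical in every school.
3. Obtain consent with a single form and complete baseline in all 20 schools.
4. Only then generate, or disclose, the within-district allocation (five and five in each district), and start the lectures.

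State who holds the allocation until step 4. If arms have already been disclosed, have consent and screening done by staff unaware of arm as far as possible, and acknowledge the limitation.

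In either case, record and report by school and arm the numbers approached, excluded (by reason) and declined, so that a reader can see whether enrolment differed.

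Cost: a short delay to the first intervention activities in September, and the work of keeping a recruitment log. No extra participants are needed and the stated sample size does not change.

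### The printed cluster sample-size formula is not a valid two-proportion formula: it overstates a per-arm n by a factor of about 1.55 to 1.68, though whether 138 itself is inflated cannot be determined

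*Combined protocol and SAP*

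**What the plan says.** The Sampling method section presents one formula as the source of the sample size. Inside its squared bracket stand "2(m-1)\rho + 2} + z_{\beta} \sqrt{m\rho + 1". In plain notation, the alpha term is z(1−α/2)·√(2[1 + (m−1)ρ]) and the power term is zβ·√(1 + mρ). The squared bracket is multiplied by p1(1−p1) + p2(1−p2) and divided by (p1 − p2)².

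The inputs are given as follows:

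- Type I error: z is "about 1.96 for an error rate of 0.05".
- Power: "e.g., for a power of 0.8, z_{β} is approximately 0.84". This is an example; no adopted power is stated.
- Rates: "the anticipated influenza vaccination rate is 80% in the intervention group and 50% in the control group".
- Clustering: "m is the size of each cohort, ρ is the intra-group correlation coefficient". Neither is given a value.
- Unit of n: by definition "n is the desired sample size for each cohort"; in the result, "the estimated sample size, denoted as 'n', is 138 students per school". The next sentence calls 138 the requirement for each group, yet the total of 2760 is 138 times the 20 schools.

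**The concern.** At ρ = 0 a cluster formula should reduce to the ordinary two-proportion sample size, and this one does not. The factor 2 in an alpha term belongs to the pooled-variance version, where it multiplies p̄(1−p̄) and stands in for the sum over both arms. Here the 2 is kept while the whole bracket is also multiplied by p1(1−p1) + p2(1−p2), which is already that sum. The power term carries no 2, so the formula is not a consistent two-arm total either. The two terms also use different design effects.

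This formula is the only sample-size justification in the documents, and 138, 2760 and 3036 are all presented as following from it. A reader cannot recover the stated error rate and power from it.

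**Working it through.** **The plan's own figures.** 138 × 20 = 2760 and 2760 × 1.10 = 3036 both reproduce. The 138 does not, because m and ρ are missing.

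**Inputs.** z = 1.96 and 0.84, p1 = 0.80, p2 = 0.50, all from Sampling method. Then p1(1−p1) + p2(1−p2) = 0.16 + 0.25 = 0.41, (p1 − p2)² = 0.09, and 0.41/0.09 = 4.556. For the pooled version p̄ = 0.65 and 2p̄(1−p̄) = 0.455. Values of m and ρ below are assumptions.

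**At ρ = 0.**

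- Printed: (1.96·√2 + 0.84)² × 4.556 = 3.612² × 4.556 = 59.4.
- Valid, unpooled, per arm: (1.96 + 0.84)² × 4.556 = 7.84 × 4.556 = 35.7.
- Valid, pooled, per arm: (1.96·√0.455 + 0.84·√0.41)² / 0.09 = 1.860² / 0.09 = 38.4.
- Valid, unpooled, as a two-arm total: 2 × 35.7 = 71.4.

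Read per arm, the printed value is too large: 59.4/35.7 = 1.66 and 59.4/38.4 = 1.55. Read as a two-arm total, it is too small: 59.4/71.4 = 0.83. It is right on neither reading.

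**With clustering.** The valid per-arm n is the ρ = 0 value times 1 + (m−1)ρ. Over m = 20 to 152 and ρ = 0 to 0.2, the printed formula gives 1.664 to 1.680 times the unpooled n and 1.546 to 1.561 times the pooled n. The ratio hardly moves because m and ρ enter both formulas almost proportionally.

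**Can the ratio be attached to 138?** Several assumed pairs make the printed formula return about 138:

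| m | ρ | printed n | valid unpooled | valid pooled |
|---|---|---|---|---|
| 14 | 0.10 | 138.1 | 82.2 | 88.4 |
| 138 | 0.0096 | 137.7 | 82.7 | 89.0 |

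A valid formula also returns 138 at other pairs. With m = 138 and ρ = 0.0209, 35.7 × (1 + 137 × 0.0209) = 35.7 × 3.863 ≈ 138. With m = 40, ρ of about 0.073 does the same. The documents cannot tell these cases apart.

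If 138 did come from the printed formula at 80% power, and is read per arm, the design effect at m = 138 is about 2.32. The effective n is then 138/2.32 = 59.5, and the power is about 95% (unpooled) or 94% (pooled).

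**The trial as planned** has 10 × 138 = 1380 students per arm. For 80% against 50%, with a t reference on 18 df and m = 138:

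| Assumed ICC | Design effect | Effective n per arm | Power |
|---|---|---|---|
| 0.10 | 14.7 | 93.9 | 99% |
| 0.20 | 28.4 | 48.6 | 87% |
| 0.25 | 35.25 | 39.1 | 79% |
| 0.30 | 42.1 | 32.8 | 72% |

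At m = 138 the valid unpooled requirement for 80% power is about 526 per arm at an ICC of 0.10, 1015 at 0.20 and 1505 at 0.30. The last exceeds 1380.

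**The case against.** The strongest reply is that the defect may be only a slip in printing the equation. The 138 may have come from a correct formula, the slip is conservative per arm, and the later multiplications are right. Much of this stands. It does not rescue the equation: the section says that the size was determined from it, so either 138 came from an invalid formula or the stated derivation is not the one used. Both need correcting.

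The reply does rule out several stronger readings that a reader might infer:

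- *That 138 is 1.55 to 1.68 times too large.* The ratio compares two formulas at the same inputs. Choosing m and ρ so that the printed formula returns 138, and then noting that a valid one returns less, only measures that ratio again.
- *That the plan contradicts its own stated power.* The value 0.8 is only an example, so there is no adopted power to contradict.
- *That the trial has about 95% power.* That figure belongs to 138 students per arm. At m = 138 that is one school per arm, and the matching valid n of about 83 is less than one school. The plan has ten schools per arm.
- *That 2760 exceeds the requirement.* Without ρ this is unknown, as the figure for an ICC of 0.30 shows.

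The equation was also read here from extracted PDF text. The 2 appears twice inside the root in mutually consistent places, which makes a misreading of it unlikely. The mismatch between mρ and (m−1)ρ could more easily be one.

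**Conclusion.** The printed formula is invalid. Its alpha term is doubled although the multiplier already sums both arms, and its power term uses the wrong design effect. At the example z values and 80% against 50%, it gives 1.66 to 1.68 times the valid unpooled per-arm n, or 1.55 to 1.56 times the pooled one. That statement needs no particular m or ρ within the range tried. It does assume that n is per arm and that power is 80%; at ρ = 0 and 90% power the unpooled ratio is 74.8/47.9 = 1.56.

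Whether 138 is inflated is undetermined. The figures of 82 to 89 per arm and 94 to 95% power hold only if 138 came from the printed formula at 80% power and is read per arm. They do not describe the planned trial, whose power depends on the unstated ICC. The flaw lies in the justification and does not show that the trial is too small or too large. Confidence is moderate, pending a check of the equation in the source.

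**What to change.** 1. Check the equation against the source PDF.
2. Replace it with n per arm = (z(1−α/2) + zβ)² × [1 + (m−1)ρ] × [p1(1−p1) + p2(1−p2)] / (p1 − p2)², or with the pooled version, and define n as per arm throughout.
3. State the m, ρ and power actually adopted, with the basis for ρ, and recalculate.
4. Keep the 20 schools. Restate the justification as the power, or the detectable difference, that 20 schools of 138 deliver over a range of ICC, using 18 df.
5. Do not describe 2760 as exceeding the requirement until ρ is given.

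The cost is protocol wording and one recalculation. Correcting the formula does not in itself call for more enrolment. Whether 1380 per arm is enough is a separate question that the stated ρ will answer.
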